Capture of DAOOH Endpoint: Each study site uses an electronic health record with time stamps for ED arrival, time leaving the ED, time of arrival to SSU or inpatient admission, and time of discharge. Thus, exact times, rounded to the nearest hour, will be calculated to determine length of stay. Any time spent in the ED, SSU, or inpatient admission will count against their DAOOH. Although the endpoint uses the term "hospital," for the purposes of this analysis and its patient-centered focus, any time in these three hospital settings (ED, SSU, inpatient admission) will be counted. If a patient returns to the hospital or to the ER, the time spent (in hours) will be added to their total length of stay. This time does not need to be consecutive.

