Given the difficulty of obtaining costs and payments, we will standardize hospitalization and SSU costs using Medicare reimbursement rates (See Sensitivity Analysis Section below). Patient costs will include self-reported out-of-pocket costs and time costs using a modified version of a previously published survey. (see attached) One limitation of self-reported data will be potential mismeasurement due to recall bias. Should the patient-completed survey lack a sufficient response rate for outpatient analysis, we will limit our analysis to the hospital portion of the treatment. Effectiveness will be defined by SF-12 and SF-6D metrics of patient self-reported QOL. The SF-12 has been previously used to evaluate outcomes for HF patients.³ Effectiveness in ICER computations is often measured using quality-adjusted life years (QALYs), defined as:

$$QALY = \sum_{t=t_0}^Z \delta^{t-t_0} q_t P_t$$

where P_t is the probability of surviving to each year t , q_t is the preference weight, and δ is the time-discounting factor. As the SF-12 does not allow direct assessment of QALYs, we will convert the score into a SF-6D preference based score using the six health dimension scores from the SF-12^{4,5} to generate the preference weights and probabilities necessary to conduct the cost-utility analysis. Since the participant will be completing the SF-12 survey at the beginning and end of the episode, all models estimating the effectiveness will include the baseline score in the vector of participant characteristics. Aside from cost and effectiveness, we will analyze the incidence of re-admission, the utilization of outpatient care, and caregiver burden, as detailed in our statistical analysis plan. While the incidence of re-admission will be obtained from both the electronic health record and patient self-report, the outpatient and caregiver burden are self-reported.

For each outcome variable of interest (patient costs, hospital costs, total episode costs, SF-12 scores, SF-6D scores, QALYs, incidence of readmission, total days of hospitalization, utilization of outpatient care, nursing care, and caregiver burden) we will estimate a predictive model accounting for the heterogeneity among participants in the intervention and control groups.

$$Y_i = \alpha + \beta_1 SSU_i + \beta_2 D_i + \beta_3 R_i + \beta_4 D_i * R_i + \beta_5 D_i * SSU_i + \beta_6 R_i * SSU_i + \beta_7 D_i * R_i * SSU_i + \gamma X_i + \delta H_h + \kappa_h + \tau_t + \varepsilon_i$$

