10.4.3.1 ADDITIONAL ANALYSES

Exploratory Analyses: As observation is not an admission, payers cover out of pocket costs differently.

Guideline Adherence: Adherence to HF guidelines at time of discharge in the SSU arm is equivalent or better than adherence in the usual care arm.

Sample Size Calculation: We assume that the adherence percentage is 85% in the control arm.⁶⁴ With 240 subjects in each arm, we will have 80% power to detect an absolute improvement of 8% in the SSU arm, where the type I error rate is controlled at 0.05 (two-sided). Adherence to HF-Guidelines will be assessed based on the established Get-With-The-Guidelines HF (GWTG-HF) metrics for eligible patients. These measures have been previously well established.^{64,74}

HF Guideline Adherence Analysis: Fisher's exact test will be used to compare the percentage of adherence. Please see below regarding sensitivity analysis and missing data approaches.

CB Scale: Sample size (both arms combined)	% of data attrition	Effect size in CB scale
480	10%	0.25
360	33%	0.30
240	55%	0.37
120	78%	0.51

Caregiver Burden Analysis: This will be similar to the KCCQ analysis. See table for sample size considerations.

Sub-group analysis: The nature of the sub-group analysis is exploratory and will be used to generate hypotheses for future testing. We will study four pre-specified sub-groups: 1) older patients, defined as greater than 75 years old; 2) gender; 3) race and 4) insurance status (Medicaid, self-pay, Medicare, Commercial). The rationale for selecting these sub-groups is based either on known cardiovascular disparities or there is limited data regarding an SSU strategy in these specific subgroups.⁴⁶ The hypothesis: there will be no differences in outcomes, QoL, or guideline adherence between any of these groups. If the primary endpoint is achieved, we aim to demonstrate the AHF SSU strategy is broadly applicable across all subgroups. If there are differences, however, this may either demonstrate areas in need of further study, or initial subgroups to target. To test these hypotheses, we will compare the treatment benefit between sub-groups by formal two-sample testing procedures using normal approximation (e.g. Z test). A permutation test will also be performed as a sensitivity analysis. Given the limited sample size and the exploratory nature of the sub-group analysis, no multiple comparison adjustment will be made for these tests.

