Intervention Monitoring: To ensure fidelity of each component of the intervention between study arms, we will also measure the following individual components of the intervention throughout the trial at both the site and overall study level: 1) Baseline patient characteristics, 2) Medicine reconciliation 3) Guideline-HF adherence 4) SSU AHF protocol adherence, 5) admission rates from the SSU 6) Quality of Life/Caregiver Burden Questionnaire response and completeness, 7) Hospitalized patients discharged within 48 hours, and 8) Follow up completed at 30 days. These analyses will be reported every 3 months to the Steering Committee to allow for course correction as needed. In addition, these will be reported at the conclusion of the study as well as at quarterly enrollment milestones to the DSMB.

Sensitivity Analyses: Some baseline covariates such as co-morbidities, medications, renal function, serum sodium, potassium, b-type natriuretic peptide (BNP) or NT-pro BNP, and blood pressure, may not be well-balanced between the two arms despite randomization. These covariates are known markers of risk in AHF patients and are part of the standard assessment for the vast majority of AHF admissions. We will use the inverse probability weighting approach to adjust those covariates with poor balance between the arms as part of a sensitivity analysis.⁷⁵ We will then compare these results with those from the two-sample t test. In addition, if the DAOOH, QoL, caregiver burden, or mRUQ-HF endpoints are found to be non-normal in distribution, the Wilcoxon Rank-Sum test will be used for comparison as a sensitivity analysis.

Modified Resource Utilization Questionnaire for Heart Failure (mRUQ-HF).⁷⁰ The mRUQ-HF is a 14-item self-report questionnaire of comprehensive lists of choice related to healthcare utilization. (See Appendix trial protocol) Exploratory analysis will occur in two steps: 1) Determination of resources consumed or related; 2) Assignment of 'value' to the resources consumed.⁷¹ This two-step process allows for transparency of assigned costs. Hospital costs will be assigned per individual hospital cost-accounting. Where monetary values are not directly self-reported, Medicare fee schedules will be used for uniformity. This will be captured at 90 days and will include the hospitalization when patients answer the questionnaire.

All Cause Mortality and All-Cause Rehospitalization Endpoints:

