10.5 SAMPLE SIZE

A one-day difference in the length of hospital stay is a 20% reduction in the mean length of stay(LOS) of five days during hospitalization (median LOS =4.3 days).⁵⁰ Pilot data support the clinical significance of a one-day reduction,⁴⁵ and discussions with patients and caregivers confirms this finding. *While we anticipate achieving greater than a one-day difference, we have powered our study conservatively.*

$$N (\text{total}) = 534; \quad N_1 = 267; \quad N_2 = 267$$

Based on published data,⁴⁶ we project that DAOOH has a mean of 25.6 with a standard deviation of 3.9 in the control arm. A reduction of the mean DAOOH by one-day is the minimal clinically meaningful difference as determined through our patient engagement outreach.⁵⁴ An interim analysis when half of the outcome data are available will be performed. (See DSMB, section E6). Accounting for this with the O'Brien-Fleming spending function, 240 subjects per arm are required to achieve 80% power in detecting the one-day difference in DAOOH, where the two-sided type I error rate is controlled at 0.05. Assuming 10% attrition due to drop-outs and lost to follow up, this study requires a total of 534 subjects. This power calculation also takes into account a conservative estimate of 40% of patients being admitted to the hospital from the SSU arm. *DAOOH automatically accounts for death.* The maximal number of days alive and out of the hospital through 30 days post randomization is 30 days. If a patient were to die on day 8 post-randomization, her DAOOH would be 8. This would be compared to a patient who stayed in the hospital 3 days after randomization, but never returned to the ED or hospital or died through 30 days. DAOOH of this patient would be 27. If the same patient returned to the hospital on day 12 for 2 days, and again on day 24 for 2 days, their total DAOOH would be 23.

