0 Did Not Change 1

2

3 Changed for the Best

OBERST CAREGIVING
BURDEN SCALE.docxBCOS120715 -
modified HF.doc**17.3 MRUQ-HF**

MODIFIED RESOURCE UTILIZATION QUESTIONNAIRE FOR HEART FAILURE
(SOCIETAL PERSPECTIVE)

This is a series of questions about your health care that you have received during **past 3 months**.

1. During the **past 3 months**, how many times have you had **appointments or visits** at any of the following clinics or providers?

Clinics / Providers	Number of Appointments/Visits	How Long (hours)	Reason for Appointments/Visits
Cardiologist			
Home health services			

Nurse clinic visit			
Emergency department			
Hospitalization			
Other healthcare appointments			
Endocrinologist			
Nephrologist			
Ophthalmologist			
Allergist/Ear Nose Throat clinic			
Alternative/ homeopathic medicine			
Chiropractor			
Dentist			
Dermatologist			
Family physician/ internal medicine/ primary care physician			
Gastroenterologist			
Mental health professional			
Orthopedist			
Physical therapist			
Physician assistant			
Podiatrist			
Other:	—		

2. Not including the visits just listed, during the **past 3 months**, how many times did you communicate (**telephone, e-mail, text, fax**) with anyone (physician, nurse, or technical support) regarding your heart condition?

	Reason for contact	Number of contacts for information needed or communication	Type of communication (phone, e-mail, etc)
Physician			
Nurse practitioner			
Nurse educator			
Social worker			
Technical (e.g., pacemaker company)			

Other:			
--------	--	--	--

3. Within the **past 3 months**, have you been visited in your home for **heart failure education**, attended a class, or a support/informational group? Yes No

3a. If **yes**, how long was each educational session and who participated in the education process with you.

	Purpose	Length of Session	How many times	Who participated with (spouse/child/sibling/other)
Visited at home				
Attended a class				
Heart failure support group				
Other:				

4. Within the **past 3 months**, have you or other family members attended **mental health counseling** sessions for support? Yes No

4a. If **yes**, how long was each counseling session and who participated in the process with you.

	Purpose	Length of Session	Who participated with (spouse/child/sibling/other)
Session 1			
Session 2			
Session 3			
Session 4			

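### Question 1 of the mRUQ-HF has no row for an observation or short-stay-unit stay, so self-reported use by setting depends on how SSU patients label the index stay

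*Combined protocol and SAP*

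**What the plan says.** The mRUQ-HF is listed in section 4.2.3 as an exploratory endpoint. Its introduction reads "This is a series of questions about your health care that you have received during" and sets a recall period of three months. Question 1 then asks how many visits the patient had "at any of the following clinics or providers", with columns for number, hours and reason. The rows include Emergency department, Hospitalization, "Other healthcare appointments" and a write-in Other line. There is no row for an observation unit or SSU.

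Section 10.4.3.1 says of this form: "This will be captured at 90 days and will include the hospitalization when patients answer the questionnaire". The same section opens its exploratory analyses with "As observation is not an admission, payers cover out of pocket costs differently". The analysis has two steps: first establish which resources were used, then attach a value to them. Hospital costs come from each hospital's own cost accounting, and Medicare fee schedules supply values that patients do not report.

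Section 10.4.2 handles the primary endpoint differently. It takes times from the electronic record and treats the three settings separately: "Any time spent in the ED, SSU, or inpatient admission will count against their DAOOH".

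Section 10.5 gives the planning value for crossover to inpatient care: "This power calculation also takes into account a conservative estimate of 40% of patients being admitted to the hospital from the SSU arm".

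**The concern.** The trial compares an SSU stay with an inpatient stay, and the utilization form names only the inpatient stay. A usual-care patient has an obvious row for the index stay. A patient discharged home from the SSU does not. By the plan's own statement the stay is not an admission, and section 10.4.2 treats the SSU as distinct from the ED. The patient has to choose a label or leave the stay out, and no section says how the answer is to be coded.

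At stake is the first step of the mRUQ-HF analysis: counts and hours by setting. For the index stay, the labelling problem arises almost only in the SSU arm, so it acts on the between-arm comparison instead of adding equal noise to both arms. Observation stays after discharge also have no row, in either arm. Exclusion criterion 1 (section 5.2) shows that some institutions require recently hospitalized patients to be observed, so such stays are foreseeable.

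**Working it through.** The documents give no sample size, power or expected difference for the mRUQ-HF, so there is no stated figure to reproduce. The size of the labelling effect can be worked out from the plan's admission rate and one assumption.

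**Inputs**
- a = 0.40, the share of the SSU arm admitted from the SSU (section 10.5). The SSU-only share is 1 - 0.40 = 0.60.
- p = the share of SSU-only patients who enter the stay in the Hospitalization row. This is an assumption, varied from 0 to 1.
- Usual care: 1.0 index hospitalization per patient, assuming that all report it.
- 240 evaluable patients per arm (section 10.5), used only to express the result as a number of entries.

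**True value.** If observation is not an admission, an SSU-only patient has no index hospitalization. The SSU-arm mean is 0.40, and the true difference is 0.40 - 1.0 = -0.60 per patient.

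**Value the form would show.** The SSU-arm mean is a + (1 - a)p = 0.40 + 0.60p. The difference from usual care is 0.40 + 0.60p - 1 = -0.60(1 - p). The error against the true value is 0.60p.
- p = 0: -0.60, or 0.60 × 240 = 144 fewer entries. This is the correct count.
- p = 0.5: -0.60 × 0.5 = -0.30, or 72 fewer entries.
- p = 1: 0, and the real difference disappears.

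**Other admission rates.** Section 10.5 calls 40% conservative. With an assumed a = 0.20, the difference is -0.80(1 - p), which runs from -0.80 to 0.

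**Double entry.** If every SSU patient calls the SSU stay a hospitalization, and the 40% who are admitted also list the inpatient stay, the SSU-arm mean is 1.0 + 0.40 = 1.40. The difference is then +0.40, with the sign reversed.

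**Hours.** The SSU stay is defined as under 24 hours (section 6.1.1). The hours moved into the Hospitalization row are therefore below 0.60 × p × 24 = 14.4p per SSU-arm patient, or 7.2 at p = 0.5. Relabelling moves hours between rows and leaves the total over all rows unchanged. The total falls only if the stay is omitted.

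**Recall window.** Section 7.3.3 allows the 90-day call from day 60 to day 120 after discharge. Three months is about 91 days, so for later calls the index stay lies outside the recall period in either arm. The usual-care value of 1.0 is thus not assured.

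**The case against.** The strongest reply is that this is an exploratory self-report item and that the important measures do not rest on it. DAOOH uses EHR time stamps (section 10.4.2). Readmission is taken from the EHR as well as from the patient (section 10.4.3). ED visits, hospital days and readmission are a separate line in the schedule of events (section 7.3.7). The form also allows recovery: it has a write-in row with hours and reason columns, follow-up is by telephone, and allocation is known, so staff could clarify the entry or recode it. All of this stands and limits the point to self-reported use by setting. It does not remove the point, because no coding rule is written and a write-in row still leaves the label to the patient.

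A reader might infer more, in four ways that the documents do not support.
- *The whole range from -0.6 to 0 is an artefact.* It is not. With observation not counted as admission, -0.6 is the true difference, and only the shrinkage toward 0 is error.
- *The index stay would be mispriced.* Section 10.4.3.1 takes hospital costs from hospital cost accounting, and no section prices a stay by the row ticked. The charge gap quoted in section 2.2 therefore cannot be multiplied by the share of relabelled stays.
- *The cost-effectiveness result is biased.* Section 10.4.3 refers to a modified published survey for patient costs without naming the mRUQ-HF. That analysis, as a secondary endpoint, covers 30 days, and Question 1 asks for no money amount. The link is only inferred.
- *A skilled-nursing row is missing too.* Section 10.4.3 does list "utilization of outpatient care, nursing care, and caregiver burden" among the modelled outcomes. But nursing care is not defined there, the grid has rows for home health services and nurse clinic visits, and exclusion criterion 9 removes patients expected to need a skilled nursing facility or inpatient rehabilitation.

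**Conclusion.** The gap is real and narrow. The form cannot identify the setting being tested, and the plan has no rule to make up for it. At the planned 40% admission rate, the true difference of about -0.6 index hospitalizations per patient would be reported as -0.6(1 - p), anywhere between -0.6 and 0, or up to +0.4 if admitted SSU patients list both stays. This rests on three assumptions: that observation is not an admission, as section 10.4.3.1 states; that all usual-care patients report their index stay; and a value of p that the documents do not supply.

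The affected quantities are self-reported counts and hours by setting, and total hours only where the stay is omitted. The primary endpoint and the hospital cost of the index stay are unaffected. This is an inexpensive improvement to an exploratory measure and does not threaten the main result.

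**What to change.** 1. Add a row for an observation or short stay unit to Question 1.
2. Take the setting and hours of the index stay (ED, SSU and inpatient) in both arms from the EHR time stamps already collected for DAOOH.
3. Instruct patients to report only stays after the index discharge, by setting. This also removes the dependence of the index stay on the three-month recall period.
4. For forms already completed, reclassify the index stay from the EHR before analysis.

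The cost is one row and one instruction on the form, a merge with data already held, and recoding of earlier forms.

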5. Approximately how much did you spend for **purchase or rental of health care-related equipment/medications** for your health care over the **past 3 months**?

Item related to heart failure	Where purchased (mail order, pharmacy, or clinics)	Cost that your insurance did not cover
Medication		
Scale for weighing self		
Oxygen		
Heart failure device		
Batteries for device		
Alcohol wipes		
Dressing tape		
Item related to other conditions	Where purchased (mail order, pharmacy, or clinics)	Cost that your insurance did not cover
Other medication		
Blood glucose meter		
Test strips		
Lancets		
Insulin (include all types)		
Insulin pen		
Insulin pump reservoirs and cartridges		
Insulin pump infusion sets		
Batteries for pump / meter		
Infusion set inserter		
Continuous glucose monitor		
Continuous glucose monitor sensor		
Ketosticks		
Supplies / food to treat hypoglycemia		
Pump accessories		
Medic alert bracelet or necklace		
Other supplies:		

Item related to mobility	Where purchased (mail order, pharmacy, or clinics)	Cost that your insurance did not cover
Wheelchair		
Scooter		
Walker		
Cane		
Hospital bed		
Ramp		
Shower chair		
commode		
Other:		

6. Do you receive your health insurance from an employer? Yes No

6a. What is your **annual** health insurance premium cost? \$_____

6b. What is your **annual** health insurance deductible? \$_____

The following questions ask about the effect of your health problems on your ability to work and perform regular activities during **past 3 months**. Please fill in the blanks or circle a number, as indicated.

7. During the past 3 months, how much time (minutes) **each week** did you spend taking your medications, following your diet (making choices and eating), and weighing yourself? _____ minutes

8. During the past 3 months, how much time was spent taking care of technical issues (such as caring for heart related equipment)? _____ minutes

9. Are you currently employed (working for pay)? Yes No Retired

► If you answered '**No**' or '**Retired**', skip Questions 10 ~ 13 and go to Question 14.

10. During the past 3 months, have you been absent from work because of illness?

Yes No

10a. If **yes**, how many days? _____, partial days: _____

11. During the past 3 months, how many hours did you actually work? _____ hours

12. Does your workplace employ a nurse? Yes No

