12a. If **yes**, during the past 3 months, how much time (minutes) did you spend in the nurse's office during the day? _____ minutes

12b. How many days per week? _____ days

13. During the past 3 months, how much did your health problems affect your productivity *while you were working*?

(Think about days you were limited in the amount or kind of work you could do, days you accomplished less than you would like, or days you could not do your work as carefully as usual. If your health problems affected your work only a little, choose a low number. Choose a high number if health problems affected your work a great deal.)

Consider only how much *your heart failure* affected productivity *while you were working*. Circle a number.

Health problems had no effect on my work						Health problems completely prevented me from working				
0	1	2	3	4	5	6	7	8	9	10

14. During the past 3 months, how much did your health problems affect your ability to do your regular daily activities, other than work at a job?

(By regular activities, we mean the usual activities you do, such as work around the house, shopping, child care, exercising, studying, and so forth. Think about times you were limited in the amount or kinds of activities you could do and times you accomplished less than you would like. If your health problems affected your activities only a little, choose a low number. Choose a high number if health problems affected your activities a great deal.)

Consider only how much *your heart failure* affected your ability to do your regular daily activities, other than work at a job. Circle a number.

Health problems had no effect on my daily activities						Health problems completely prevented me from doing my daily activities				
0	1	2	3	4	5	6	7	8	9	10

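### The mRUQ-HF asks about 3 months of work loss only if the patient is employed when completing it, so patients who stopped work within those months are never asked

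*Combined protocol and SAP*

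**What the plan says.** Question 9 of the mRUQ-HF (section 17.3) reads "Are you currently employed (working for pay)? Yes No Retired". Those answering No or Retired are told to "skip Questions 10 ~ 13 and go to Question 14".

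The gated items use a longer time frame than the gate:

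- Question 10: "During the past 3 months, have you been absent from work because of illness", with a count of full and partial days.
- Question 11: "During the past 3 months, how many hours did you actually work".
- Question 12a: minutes spent with a workplace nurse over the same period.
- Question 13: "During the past 3 months, how much did your health problems affect your productivity" while at work.

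The next item that everyone answers, Question 14, asks how far health problems "affect your ability to do your regular daily activities, other than work at a job".

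Section 10.4.3.1 places the questionnaire at 90 days and intends it to take in the hospitalization. Section 10.1.1 gives it a societal perspective, and section 4.2.3 lists it as exploratory. Section 10.4.3 says of the cost analysis: "Patient costs will include self-reported out-of-pocket costs and time costs using a modified version of a previously published survey". Section 10.4.5 provides multiple imputation under missing at random for incomplete data and says nothing about items skipped by design.

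**The concern.** The gate refers to one day and the questions behind it to 3 months. A patient who was working at the index ED visit and then resigned, lost the job or retired because of heart failure answers No or Retired and never reaches the work items. Such patients probably have the largest work losses in the trial. The top of the 0 to 10 scale in Question 13 stands for being wholly unable to work because of health, which describes many of them, yet the gate removes them before they see it.

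Leaving work happens after randomization and may itself be an effect of the care strategy. Who contributes work-loss data then depends on an outcome. Two consequences follow for a societal cost estimate: time costs are too low in total, and the difference between arms is distorted if leaving work is more common in one arm.

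**Working it through.** The documents state no figure for lost work, so there is nothing to reproduce. The check is of the skip logic, followed by illustrations under stated assumptions.

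**1. Can another item recover the loss?**

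| Source | What it gives | Recovers paid-work loss? |
|---|---|---|
| Question 6 | Employer insurance, premium, deductible | No: neither work status nor days |
| Questions 7 and 8 | Time on self-care and equipment | No |
| Question 14 | Daily activities, paid work excluded | No |
| Schedule of events (7.3.7) | No employment row at baseline or later | No |
| Caregiver scales (17.2) | Caregiver tasks and life changes | No |

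**2. Do the analysis rules repair it?** The imputation in 10.4.5 has nothing to work from. Among patients answering No or Retired, the form does not separate someone retired for ten years, whose true work loss is nil, from someone who stopped last month. Imputing from employed patients would assign work loss to both. The fallback in 10.4.3, which confines the analysis to the hospital portion if survey response is insufficient, would not be triggered, because a form that follows the skip rule is complete.

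**3. Days missed per affected patient.** Assumptions: 3 months is 90 days; the patient worked until the index event and not after discharge. Section 7.3.3 allows the call at 90 ± 30 days, that is, 60 to 120 days after discharge. Workdays not asked about = days after discharge inside the recall window × workdays per week / 7.

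- 5 days a week, call at day 60: 60 × 5/7 ≈ 43.
- 5 days a week, call at day 90 or later: 90 × 5/7 ≈ 64.
- 2 days a week: 60 × 2/7 ≈ 17 to 90 × 2/7 ≈ 26.

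The form captures none of these days.

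**4. Number of such patients.** The sample size in 10.5 implies 2 × 240 = 480 evaluable patients. Assume that 10–30% work at entry and 5–10% of those leave: 480 × 0.10 × 0.05 = 2.4, up to 480 × 0.30 × 0.10 = 14.4. That is about 2 to 14 patients over both arms. Both percentages are assumptions.

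**5. Why the treatment of blanks matters.** Assume that leavers lose 45 days, those still employed miss 10, and 5% leave in arm A against 10% in arm B. Mean days lost per patient working at entry:

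| | Arm A | Arm B | B − A |
|---|---|---|---|
| All losses counted | 0.05×45 + 0.95×10 = 11.75 | 0.10×45 + 0.90×10 = 13.5 | +1.75 |
| Leavers dropped | 10 | 10 | 0 |
| Leavers valued at zero | 0.95×10 = 9.5 | 0.90×10 = 9.0 | −0.5 |

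With equal leaving in the two arms and the same days per patient, all three rows give a difference of zero, and only the total is too low.

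**The case against.** The strongest reply is that this is a small matter of instrument design in a published questionnaire, used for an exploratory measure of healthcare use. The plan defines no work-loss endpoint, never says that time costs means lost work, and already warns in 10.4.3 that costs outside the hospital may be incomplete. A patient on sick leave may answer Yes and be captured. Rewording an item during the trial has its own cost. All of this limits the importance of the point and argues for leaving Question 9 as it is. It does not remove the mismatch between gate and recall period.

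Four stronger readings are tempting, and the documents do not support them.

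- *The form records no lost work for these patients.* It does not: the instruction is to skip, so the fields are blank. A zero arises only if the analyst assigns one, and the plan gives no rule either way.
- *The loss cannot be recovered from any trial record.* This is established only for the forms and schedule rows shown. The case report forms, the KCCQ and the SF-12 are not reproduced.
- *The cost comparison points the wrong way.* A reversal needs both unequal leaving between arms and blanks valued at zero. The plan specifies no work-loss comparison, and the secondary cost-effectiveness endpoint covers a 30-day episode, whereas this questionnaire is taken at 90 days.
- *A given share of all lost workdays is missed.* With 45 and 10 days as above, the share is leave × 45 / (leave × 45 + (1 − leave) × 10): 4% at 1% leaving, 8% at 2%, 19% at 5% and 33% at 10%. Since no input comes from the trial, none of these can be put forward as an estimate.

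**Conclusion.** The point holds as a minor design flaw. The current-status gate excludes patients who left work inside the recall window, nothing shown elsewhere captures their loss, and the plan is silent on how the blanks are valued. The patient time-cost component of the exploratory 90-day societal analysis is therefore understated as collected, with possible bias between arms if leaving work differs.

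This rests on two readings: that the survey named in 10.4.3 is the mRUQ-HF, the only resource-use questionnaire reproduced, and that time costs include lost work. The loss may be large for an individual, but its total cannot be derived and probably comes from few patients. The primary endpoint (DAOOH), the sample size and the hospital/payer cost analysis do not depend on it.

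**What to change.** Keep Question 9 as worded. For patients answering No or Retired, add: *Did you work for pay at any time in the past 3 months? If yes, when did you stop, and was it because of your health?* Then:

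- Route those answering yes to Questions 10 to 13.
- Count workdays lost after a health-related stop only within the fixed 3-month recall window. Counting up to the call would tie the cost to a call date that can vary by 60 days.
- State in section 10.4.3 how skipped work items are valued. Treat forms already completed with No or Retired as work loss unknown, not zero. Reporting results with and without those patients would recover nothing, since none of them has answers to Questions 10 to 13.

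One limit remains. A patient who stopped at the index visit and is called at day 90 or later may truthfully say that no work was done in the past 3 months. Adding *or when you came to the emergency department for this study* to the item would cover that case.

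The cost is one added line, a minor IRB amendment (section 12), two form versions in the data, and slightly less comparability with other uses of the questionnaire. If data collection is complete, only the valuation rule can still be adopted.
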